2 INTRODUCTION

2.1 STUDY RATIONALE

Nonalcoholic fatty liver disease (NAFLD) has quickly become the most common liver disease in children in the US and is rising worldwide^{1,2}. While the true prevalence and incidence are not known, estimates have placed prevalence in the US as high as 7 million children¹. The prevalence varies greatly across race and ethnic groups with Hispanic, Asian and White children having increased rates compared to African American children^{3,4}.

Similar to adults, NAFLD ranges widely in severity in children. Cases of cirrhosis and end stage liver disease have been rarely reported. Most children have some fibrosis present on liver biopsy, however the majority have mild fibrosis (stages 1-2) and advanced fibrosis is less common (found in 3-15%)^{5,6}. Nonalcoholic steatohepatitis (NASH) is considered the more severe form of NAFLD and is a pathologist's assessment that the biopsy has features of steatosis, inflammation and hepatocyte ballooning⁷. NASH is seen less often in children because children rarely exhibit hepatocyte ballooning; thus even with substantial levels of inflammation, the threshold of NASH is not met⁸. Children more often have a portal pattern of inflammation, called portal predominant or type 2^{6,9}. This portal pattern disappears by late adolescence and is rarely seen in adults suggesting that it is simply a juvenile inflammatory response pattern¹⁰. The type 2 portal pattern does not appear to be predictive of future histopathology or clinical course.

ALT elevation is the most common screening test used for detecting NAFLD. A normal ALT in boys and girls is <26 U/L and <23 U/L respectively¹¹. Similar to adults, very mild elevations in ALT or even normal ALT can be found in NAFLD¹². Children with a sustained ALT \geq 80 U/L are twice as likely to have NASH^{8,13}. The typical diagnosis algorithm is complicated because NAFLD is a diagnosis of exclusion and no single test can determine it. Typically, serologic tests are sent to rule out other chronic liver diseases and including other causes of steatosis. Ruling out chronic alcohol use is critical in adults but less relevant in a pediatric cohort. After other chronic liver disease screening tests are performed, either an MRI or liver biopsy is used to detect the presence of steatosis in the liver. Ultrasound is less useful because of its low sensitivity and specificity. Magnetic resonance imaging (MRI) methods including MR spectroscopy and MR proton density fat fraction and MR volumetric fat fraction are all highly sensitive, specific and precise^{14,15}. Liver biopsy has been considered the gold standard but it is less accurate for measuring fat in the liver because of the small sample size and subjective nature of the pathologist's estimate of steatosis. Liver biopsy is the best method for detecting NASH because it demonstrates all the necessary criteria (steatosis, inflammation and hepatocyte ballooning)⁸. Fibrosis is also best measured through liver biopsy at this time, although multiple non-invasive imaging methods are being developed in an attempt to replace it⁸.

The pathophysiology of NAFLD is complex and mirrors the wide variety of clinical phenotypes. There is clearly a genetic background that is the basis for developing NAFLD^{16,17}. However, presence of one of these polymorphisms is not sufficient to develop NAFLD. There appears to be one or more environmental triggers that induce the phenotypes of NAFLD. These environmental triggers are a subject of intense research effort. One of the top suspects in the environment is the hypercaloric diet¹⁸. Others include environmental toxins such as plastics, air pollution, heavy metals etc. Lastly, changes in

the nutrient content such as a high sugar diet or a diet low in antioxidant supply may contribute^{19,20}. The timing of exposure may be critical and newer research points to the in utero time period as a critical time for triggering steatosis in the liver of children²¹.

NAFLD is not simply a liver disease and in fact, the critical driver of NAFLD may be outside the liver. The best evidence for this is the rapid reoccurrence of NAFLD after liver transplant, suggesting that the milieu that the new liver is placed into is still NAFLD-genic. NAFLD appears to be a systemic lipid dysregulation with evidence of maladapted lipid flux throughout the body. NAFLD occurs in the setting of both hepatic and whole-body insulin resistance²². Adipose insulin resistance is strongly associated²³. Within the liver, de novo lipogenesis (DNL) is inappropriately upregulated in NAFLD, resulting in increased synthesis of triglycerides from carbohydrates and other sources²⁴. Increased triglycerides are exported out of the liver on large, overloaded very low-density lipoprotein (VLDL) particles resulting in dyslipidemia and resultant atherosclerosis. Increased visceral fat is closely linked to hepatic steatosis, although it appears that hepatic steatosis is more closely related to insulin resistance compared to visceral fat. Adiponectin, a beneficial hormone secreted from healthy adipose tissue is deficient in NAFLD²⁵.

The long term natural history of NAFLD beginning in children is not yet known because the past and current cohorts of children have not been followed long enough to assess rates of liver outcomes such as cirrhosis, hepatocellular carcinoma and portal hypertension. However, sufficient evidence exists to warrant concern. For example, rates of liver transplant for NAFLD in young adults is rapidly increasing²⁶. And importantly, the incidence of type 2 diabetes in children with NAFLD is 10 x the expected rate of diabetes onset in children^{27,28}. Type 2 diabetes may be the more important clinical outcome of NAFLD for children because pancreatic beta cell failure (diabetes) foretells a lifetime of morbidity including future health decline from kidney disease, vision loss, cardiovascular events and more. In children, those with NASH are more likely to have diabetes²⁸. In adults with NAFLD, the most frequent cause of mortality is cardiovascular disease (CVD). Because of this, any medication developed for children with NAFLD should have long term CVD safety and/or benefit on cardiovascular risk markers.

The current standard of care for treating NAFLD in children is lifestyle changes⁸. There are not specific recommendations for a best diet or exercise goals because of the lack of randomized controlled trials in children with NAFLD, so the approach is based on an accumulation of evidence from case series, small trials and studies in obese children (not necessarily with NAFLD). Sugar reduction appears to be a potent and important component of diet improvement for treating NAFLD. Other treatments with limited evidence including metformin and vitamin E. Both were tested in a large RCT in children and did not meet the primary outcome of improved ALT, however both resulted in some significant histologic improvements in children with biopsy proven NASH²⁹. A more recent trial testing cysteamine bitartrate delayed release in children with NAFLD failed to meet the primary outcome of a 2-point improvement in NAFLD activity score (NAS) although improvement was seen in ALT, particularly in younger children³⁰.

One of the challenges in therapeutic development for NAFLD is the lack of validated surrogate markers of clinical benefit. Because the natural history in children is not known, the target for clinical benefit is also not clear, although perhaps a case could be made for avoiding type 2 diabetes. Most trials to date in both pediatrics and adults have focused on improvement in either liver histology (a surrogate for future cirrhosis) or improvement in ALT (surrogate for improvement in liver histology). Both of these have substantial issues but have been accepted because of the lack of better alternative. ALT is associated with hepatic inflammation and a substantial decrease in ALT is likely to represent improvement in NASH and fibrosis on liver biopsy (Figure 1).

[figure not shown]

Figure 1. In 145 children who participated in the NIH sponsored “TONIC” trial testing metformin or vitamin E compared to placebo, there was significant association between improvement of ALT over time (from 0 to 96 weeks) and improvement in both NASH (1A) and Fibrosis (1B), $p < .05$ in both. At week 12, decreases in ALT of less than 20% were associated with failing to improve histology (progressed or stayed stable). Data submitted for publication.

MRI can be used to measure steatosis very precisely and is useful as a measurement in clinical trials in NAFLD. However, decrease in steatosis alone is not clearly a useful because of the lack of association of steatosis with longer term outcomes. Improvement in systemic metabolic measures such as insulin sensitivity, lipid levels, lipid particle sizes and adiponectin may be useful because of the close association of NAFLD with type 2 diabetes and CVD.

In summary, the rationale for this trial is as follows. NAFLD affects many children and is highly likely to lead to substantial morbidity and mortality, particularly from type 2 diabetes and cardiovascular disease. Lifestyle changes are the first line treatment, but many children fail to respond to these. Pharmaceutical treatments are needed for children that cure NAFLD and ideally also benefit the systemic features (dyslipidemia, insulin sensitivity, BMI). Gemcabene is a promising therapeutic that may benefit pediatric NAFLD and early phase trials are needed to support further development for this indication.

2.2 BACKGROUND

Introduction to Gemcabene: Gemphire Therapeutics Inc. (Gemphire) is developing gemcabene calcium (also denoted as CI-1027 or PD72953 and in this protocol referred to as gemcabene) for multiple indications including:

- 1.) As an adjunct to diet and statin therapy for the treatment of patients with dyslipidemia who require additional low-density lipoprotein cholesterol (LDL-C) lowering such as patients with homozygous familial hypercholesterolemia (HoFH) and heterozygous FH (HeFH) and atherosclerotic cardiovascular disease (ASCVD).
- 2.) To reduce triglycerides (TG) in patients with severe hypertriglyceridemia (TG \geq 500 mg/dL),
- 3.) To reduce or stop progression of hepatic steatosis in patients with nonalcoholic fatty liver disease (NAFLD)/nonalcoholic steatohepatitis (NASH).

To date 18 clinical studies evaluating gemcabene have been conducted (17 completed and 1 terminated for business reasons) evaluating a total of 1278 healthy adult volunteers and participants with 901 exposed to gemcabene providing extensive safety data and preliminary efficacy data for triglyceride reduction. No studies have previously been conducted in NAFLD populations.

Brief Mechanism of Action Summarized from Investigator Brochure Version 2: Gemcabene is the monocalcium salt of a dialkyl ether dicarboxylic acid and is a new class of lipid-regulating compounds because it has 2 terminal gem-dimethyl carboxylate moieties. It has several mechanisms of action including 1) enhancing the clearance of VLDL and 2) blocking the production of hepatic TG and cholesterol synthesis.

The enhanced clearance of VLDL is through decreased apolipoprotein C-III, an apolipoprotein that when elevated can mask apoE on VLDL remnants and inhibit LPL mediated TG lipolysis. Elevated apoC-III is associated with increased CVD risk. Gemcabene decreases apoC-III through decreased expression of mRNA, likely decreasing protein production. This leads to increased VLDL-remnant clearance and enhances LPL activity with the overall effect of lowering LDL-C and TG.

Gemcabene also has effects within the hepatocytes. In primary rat hepatocytes, gemcabene markedly blocked radiolabeled acetate incorporation into both TG and cholesterol. AcetylCoA carboxylase (ACC1) is the rate limiting step in de novo lipogenesis (DNL). Gemcabene may reduce ACC1 mRNA expression as well as inhibit ACC1 enzymatic activity, suggesting that it blocks the ACC1 step during DNL.

Gemcabene may have other anti-inflammatory effects. It reduces C-reactive protein (CRP), mRNA production and decreases CRP in animal models and in humans. It down-regulates multiple markers of inflammation. It may inhibit the activation of nuclear hormone receptors (NHR) including NF- κ B.

Gemcabene has a similar terminal gem-dimethyl carboxylate moiety to the widely used fibrate gemfibrozil and it also increases liver peroxisomal structures and enzymes in rodents, so it has been classified by the FDA as a peroxisome proliferator-activated receptor (PPAR) agonist. However, in 3 species (mice, rat, human) gemcabene has shown little or no direct agonist activity. It has shown weak PPAR- α and weak PPAR- γ activity *in vitro* and *in vivo*. In a 52-week safety study in monkeys no liver peroxisomal structures were noted in exposure of up to 4 times the exposure levels expected in the current study.

Summary of Pre-Clinical Data from Investigator Brochure Version 2:

The full details of the comprehensive program evaluating the pharmacology, absorption, distribution, metabolism, excretion, toxicokinetics, safety pharmacology and toxicology of gemcabene is available in the investigator brochure including a tabular summary of the key non-clinical safety studies. In animal models, gemcabene had the following actions:

- In LDL receptor deficient mice, gemcabene significantly reduced total cholesterol and LDL-C.
- In chow-fed Sprague-Dawley rats, gemcabene caused an increase in HDL-C and reduction of VLDL-C, LDL-C, ApoC-II, ApoC-III.
- In female, obese Zucker rats, gemcabene increased HDL-C, ApoE and decreased TG and apoC-II.
- In transgenic lipoprotein(a) mice, gemcabene significantly reduced total cholesterol, Lp(a) and ApoB-100.
- In a mouse model of NASH, gemcabene showed anti-fibrotic effects at all tested doses and demonstrated anti-NASH and hepatoprotective effects on liver pathology of STAM mice.
- In non-human primate models, gemcabene was shown to reduce Lp(a) and total cholesterol.
- In several rodent models, gemcabene decreased inflammation and pain response.

Safety pharmacology studies in mice, Wistar rats and beagle dogs demonstrated no adverse effect on central nervous system (CNS), respiratory or cardiovascular parameters.

Oral bioavailability studies have been conducted in Wistar rats and in cynomolgus monkeys. In all studies, gemcabene was rapidly absorbed following oral administration and primarily excreted in the feces of rats and in the urine of monkeys.

Single and repeated dose toxicity studies were conducted in mice, rats and monkeys. In rats, gemcabene was well tolerated up to 100 mg/kg/day. Increased liver weight, increased hepatic peroxisomal enzymes, increased fine vacuolation of hepatocytes and hepatocellular hypertrophy were observed in rats at all doses in repeat dose studies of gemcabene. In cynomolgus monkeys, administered gemcabene at oral doses of 10, 30 and 100 mg/kg/day or up to 52 weeks there were no gemcabene related deaths, clinical signs of toxicity or ophthalmologic findings, no effects on CK and no heart related changes. Decreases in body weight gain were observed in males and females at 100 mg/kg/day. Mild, partially reversible changes in red cell mass were observed in all doses and correlated with decreased cellularity of sternal bone marrow in some animals. Reversible mild increases in creatinine and BUN were seen at all doses but without histologic changes in the kidneys. Dose related increases in liver weights were observed at 10mg/kg/day in males and >30mg/kd/day in females and were associated with histologic hepatocyte hypertrophy. In the liver, in both sexes at 100 mg/kd/day there was some single cell necrosis, mild degeneration of centrilobular hepatocytes and some oval cell hyperplasia. Findings in the liver were associated with mild to moderate increases in ALT. These were reversible at the end of the 12-week recovery period except for the increase in liver weight. Based on these findings, the no observed adverse effect level (NOAEL) at up to 52 weeks exposure is 30 mg/kg/day.

While most of the toxicity data was reassuring, there was toxicity seen in a 26 week, repeat dose oral toxicity study in rats. Body weight decreased 25-46% and hemoglobin, hematocrit and reticulocyte count decreased at all dose levels (30-300 mg/kg/day). There were increases of 85% to 4.5 fold in ALT activity at the higher doses of 100 and 300 mg/kg/day. Liver weights were increased and liver pathologic changes were seen including hepatocellular hypertrophy and vacuolation. In cynomolgus

monkeys, over 26 weeks at >30 mg/kg/day fatty changes were seen in the liver and kidneys. Carcinogenicity studies are ongoing in mice and rats. No mutagenic effects were seen in genetic toxicity studies. Developmental toxicity studies demonstrated abnormalities and teratogenicity at doses >10 mg/kg/day in rats but none in rabbits.

Summary of clinical studies with Gemcabene from the Investigator Brochure Version 2:

Phase 1 PK studies have demonstrated that oral gemcabene is rapidly absorbed with exposure increasing approximately linearly with dose. The primary route of elimination is renal. There is no clinically relevant effect on QT interval. There was a rapidly reversible increase in serum creatinine that is thought to be a hemodynamic change rather than a direct nephrotoxic effect because no change in protein to creatinine ration and no abnormal urine analysis was present. No effect was observed on blood pressure. There was an increase in the glucose disposal rate.

Phase 2 Efficacy studies have demonstrated benefits. In patients with dyslipidemia, monotherapy with 300 – 900 mg significantly lowered LDL-C compared to placebo in three Phase 2 studies. In patients with baseline TG \geq 200 mg/dL (Study 1027-04), gemcabene lowered TG by 39% at the 300 mg dose compared with 5% lowering by placebo.

Human safety data is drawn from this collection of 19 clinical studies. The most frequent reported adverse events in healthy volunteers for single doses were headache, asthenia, nausea, dizziness and somnolence. The most frequent adverse events for 4 weeks were headache, infection, nausea, asthenia, photosensitivity reaction, rhinitis, diarrhea, flatulence, dizziness and pharyngitis. In patients with dyslipidemia treated for 8 weeks, headache, asthenia, dizziness and pain were more frequent with gemcabene compared to placebo at doses from 300-900 mg. Nausea, dyspepsia and flatulence were more frequent with gemcabene compared to placebo. In 1272 healthy adult volunteers and patients, only 17 discontinued due to gemcabene related adverse events. There were no treatment related serious adverse events and no deaths.

Important Literature and Data Relevant to the Trial

There are two publications reporting trials using gemcabene. The first was published in 2003 and reported the efficacy and tolerability of gemcabene in 161 patients with low HDL and high serum TG³¹. In this study, patients underwent a 6-week placebo, dietary lead in period and then were administered either 150, 300, 600 or 900 mg once daily for twelve weeks. At the 150 mg dose, HDL significantly improved and at both the 150 mg and 300 mg doses, TG significantly decreased compared to baseline. Gemcabene was well tolerated with adverse event rates similar to placebo. The second reported trial was published in 2016 and reported gemcabene as an additive therapy to statins in 61 stable hypercholesterolemic patients³². This was an 8 week, double-blind, placebo controlled, randomized, phase 2 study in men and post-menopausal women and tested Gemcabene at doses of both 300 and 900 mg. Gemcabene as an add-on to stable statin therapy demonstrated additional statistically significant reductions in LDL-C and CRP compared to placebo.

Context of the Trial

At this time, there is not yet an FDA approved medication for NAFLD in either children or adults. There have been two large, randomized controlled trials in children testing metformin, vitamin E and cysteamine bitartrate and both were negative for the primary outcomes. There is consensus in the NAFLD field that while patients respond to lifestyle treatment, it is not effective for all patients and may not cure or resolve the more severe forms including NASH and NAFLD with fibrosis^{33,34}. Thus, medications are being sought that will not only improve the histologic features of progressive disease

(inflammation, ballooning, fibrosis) but will also improve the systemic dysmetabolic features associated with NAFLD that lead to type 2 diabetes and to cardiovascular disease. The combination of these two effects is especially important for children because simply “curing” the liver expression of the disease may not provide sufficient long term clinical benefit if the subsequent consequences are in the form of type 2 diabetes and cardiovascular disease.

Importance of this Trial and Relevance

Gemcabene is a novel therapeutic with substantial safety data in humans for treatment up to twelve weeks at doses as high as 900 mg daily. The mechanisms of action are highly relevant in NAFLD including reduction of de novo lipogenesis, the key lipid malfunction in NAFLD, decrease in circulating TG and LDL-C and decrease in systemic inflammation. All of these mechanisms are altered in NAFLD and Gemcabene has the potential to ameliorate hepatic steatosis, the inflammatory response to the hepatic steatosis as well as systemic inflammation and the associated dyslipidemia. The proposed trial is a phase 2a, preliminary efficacy and safety trial in children because it has not previously been tested in children and because it has not previously been tested in patients with NAFLD. This trial will provide support for future phase 2b and phase 3 trials to prove efficacy and longer term safety in this population. Critical questions to be answered in this trial include the tolerability of gemcabene at 300 mg in a pediatric population, the effect on ALT (a biomarker of hepatic inflammation), the effect on hepatic steatosis volume and the effect on circulating lipid levels. Additional mechanistic questions remain including what happens to the excess acetyl coA after interruption of the de novo lipogenesis pathway and so exploratory studies are planned to test effect of Gemcabene on DNL, ketogenesis (the likely pathway for diverted acetyl CoA metabolites) and to test changes in whole body metabolite patterns (metabolomics).

2.3 RISK/BENEFIT ASSESSMENT

2.3.1 KNOWN POTENTIAL RISKS

The safety and efficacy profile of gemcabene has been developed through 18 Phase 1 and 2 studies including 1278 healthy volunteers and patients.

Common adverse events include:

- Headaches
- Asthenia (feeling of weakness)
- Nausea
- Dizziness
- Dyspepsia
- Abnormal bowel movements
- Myalgia (muscle pain)
- Increased BUN
- Increased creatinine

Identified and Potential Important Risks:

Based on the non-clinical and clinical safety data collected, important potential risks are liver findings, hemoglobin decrease, BUN and creatinine increase and myalgia. Importantly, only one patient had transaminase elevation > 3x ULN after receiving gemcabene 600 mg and atorvastatin 80 mg and the

percentage of transaminase elevations overall is similar to placebo. While hemoglobin decrease was seen in non-clinical toxicity studies, only small decreases in hemoglobin have been observed clinically and were also seen with placebo (not statistically significant). Small increases in creatinine and BUN have been observed in clinical studies with gemcabene. The effects were mild and appeared within the first 2-4 weeks of treatment, did not worsen over time and were not persistent and generally resolved within 10-14 days after discontinuation of gemcabene.

Other risks:

- There is a possibility of rhabdomyolysis when combined with a statin.
- Patients with a hypersensitivity to or who have a history of significant adverse reactions to any fibrate lipid lower agents should avoid gemcabene.
- Patients on potent CYP 3A4 inhibitors such as itraconazole or a macrolide antibiotic should be excluded.
- Based on non-clinical studies in rats, gemcabene should not be administered to pregnant women or women of childbearing potential not using effective methods to prevent pregnancy.
- The safety and effectiveness of gemcabene has not been established in children and juvenile toxicity studies are underway but not yet completed.
- 2-year carcinogenicity studies are ongoing and therefore potential for carcinogenic activity is still not known.

Risks from the procedures in the protocol:

Procedures in this protocol are minimized and include 1) blood draws 2) MRI and 3) IV placement for repeated blood draws. To minimize risk to the participants, all blood draws and IV placements will be performed by pediatric experience staff in the research centers. All MRI's will be without contrast and without any sedation as these are the two primary risks of MRI.

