5.2 EXCLUSION CRITERIA

An individual who meets any of the following criteria will be excluded from participation in this study:

1. Heart disease (e.g., myocardial infarction, heart failure, unstable arrhythmias)
2. Seizure disorder
3. Active coagulopathy (INR $>$ 1.4)
4. Renal dysfunction with an estimated glomerular filtration rate (eGFR) $<$ 60ml/min/1.73 calculated using Schwartz Bedside GFR calculator for children
5. History of active malignant disease requiring chemotherapy or radiation
6. History of significant alcohol intake (AUDIT questionnaire) or inability to quantify alcohol consumption
7. Use of new medications or supplements with the intent to treat NAFLD/NASH during the 30 days prior to screening, including statin therapy. Medications or supplements (including metformin and vitamin E) that they have been on and are on a stable dose are acceptable
8. History of bariatric surgery or planning to undergo bariatric surgery during study duration
9. Clinically significant depression
10. Any girl nursing, planning a pregnancy, known or suspected to be pregnant, or who has a positive pregnancy screen
11. Non-compensated liver disease defined as cirrhosis and any one of the following hematologic, biochemical, and serological criteria on entry into protocol:
 - Hemoglobin $<$ 10 g/dL;
 - White blood cell (WBC) $<$ 3,500 cells/mm³;
 - Neutrophil count $<$ 1,500 cells/mm³;
 - Platelets $<$ 150,000 cells/mm³;
 - Total bilirubin $>$ 1.3 mg/dL unless due to Gilbert's syndrome (subjects with a history of Gilbert's syndrome may be included if both direct bilirubin and the reticulocyte count do not exceed the ULN [reflexive direct bilirubin testing will be used to confirm Gilbert's syndrome])
 - Albumin $<$ 3.2 g/dL
 - International normalized ratio (INR) $>$ 1.3
 - Abnormal alkaline phosphatase
 - Any history of ascites, variceal bleeding, hepatic encephalopathy, or hepatocellular carcinoma (HCC)
12. Poorly controlled diabetes mellitus (hemoglobin A1c (HbA1c) $>$ 8%) or requiring insulin
13. Patients with type I diabetes mellitus
14. Chronic liver disease other than NAFLD
15. Patients on CYP 3A4 inhibitors such as itraconazole or macrolide antibiotics are excluded
16. Patients who are on thiazolidinediones, fibrates or fish oils are excluded

17. Patients who are on daily prescription medications are excluded except for allergy medications, ADHD medications, asthma medications, or any other acceptable medication in the opinion of the investigator

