18. Abnormal creatinine kinase levels at screening (may be repeated if the elevation is thought to be exercise related)
19. Sexually active female participants of childbearing potential and Tanner stage ≥ 4 or menstruating unwilling to utilize two acceptable forms of contraception from screening through completion of the study or unwilling to complete pregnancy tests throughout the study
20. Currently enrolled in a clinical trial or who received an investigational study drug within 90 days of screening
21. Participants who are not able or willing to comply with the protocol or have any other condition that would impede compliance or hinder completion of the study, in the opinion of the investigator

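### Section 2.3.1 warns against gemcabene in patients with fibrate hypersensitivity or a past significant fibrate reaction, but Section 5.2 has no matching exclusion

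*Combined protocol and SAP*

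**What the plan says.** Section 2.3.1 (Known Potential Risks) lists, under other risks, groups for whom gemcabene is a concern. One entry reads: "Patients with a hypersensitivity to or who have a history of significant adverse reactions to any fibrate lipid lower agents should avoid gemcabene". Section 2.2 gives some context for a fibrate warning: "Gemcabene has a similar terminal gem-dimethyl carboxylate moiety to the widely used fibrate gemfibrozil".

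Eligibility is set by the nine inclusion criteria in Section 5.1, all of which must be met, and the 21 exclusion criteria in Section 5.2, any one of which excludes. Fibrates appear once, in exclusion 16: "Patients who are on thiazolidinediones, fibrates or fish oils are excluded". The discretionary exclusion, number 21, reaches participants who cannot or will not comply with the protocol or who "have any other condition that would impede compliance or hinder completion of the study, in the opinion of the investigator".

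**The concern.** The risk section and the eligibility list address different children. The warning concerns hypersensitivity and past reactions; the criterion concerns present use. A child who reacted badly to a fibrate would normally have stopped it, is then no longer a current user, and passes exclusion 16. The child most clearly described by the warning is therefore one the criterion does not catch.

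Section 2.2 presents this as the first use of gemcabene in children, and Section 2.3.3 justifies the trial partly on the ground that risk is being minimised. A precaution that the protocol states itself, but that screening does not apply, weakens that argument. The harm, if any, would fall on an individual participant.

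**Working it through.** No arithmetic applies, because the point depends on no rate, effect size or sample size. The check is a comparison of texts.

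1. **Criteria naming fibrates.** One of the 21 exclusions does (number 16, current use). None of the nine inclusion criteria does.

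2. **Criteria naming hypersensitivity, allergy or a past reaction to a fibrate or to the study drug.** 0 of 21 exclusions and 0 of 9 inclusion criteria. Inclusion 5a uses the medical history to rule out other causes of liver disease, including hepatotoxic drugs. That serves the NAFLD diagnosis and does not ask about drug intolerance.

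3. **Fate of the neighbouring statements in Section 2.3.1.**

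| Statement in 2.3.1 | Counterpart in 5.2 |
|---|---|
| "Patients on potent CYP 3A4 inhibitors such as itraconazole or a macrolide antibiotic should be excluded" | Exclusion 15: "Patients on CYP 3A4 inhibitors such as itraconazole or macrolide antibiotics are excluded" |
| Pregnancy and childbearing potential | Exclusions 10 and 19 |
| Fibrate hypersensitivity or past reaction | None |

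The first two were turned into criteria. The third was not, and no reason is given.

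4. **Other text that might supply the rule.**
   - Exclusion 21 is about compliance and completing the study. A past fibrate reaction need not affect either.
   - Section 7.2 allows withdrawal when a participant is found to meet an exclusion criterion. With no such criterion for fibrate reactions, a reaction discovered later does not trigger that clause.
   - Section 7.2 also allows withdrawal when a medical condition makes continuing contrary to the participant's interest. That is discretionary and acts after entry.
   - The sub-study exclusions in Section 13.2 cover food allergies and a known reaction to deuterated water. So the protocol does screen for a past reaction to the tracer, but not for the one it links to the study drug.
   - The amendment history in Section 10.4 has an entry on the timing of earlier fibrate use. It concerns use, not reactions, and does not alter the current text.

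5. **Result.** A child with a past fibrate reaction who is not now taking a fibrate meets no listed exclusion on that ground.

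**The case against.** The strongest reply is that the protocol does say these patients should avoid the drug, and that only a numbered criterion is missing. Section 10.1.7 requires the protocol and Investigator's Brochure to be reviewed with the investigator and site staff before any subject is enrolled. Table 1 places medical history and concomitant medication review at Screening. An attentive investigator could well decline to enrol such a child. This stands in part: it makes inadvertent dosing less likely. It does not turn the warning into a criterion, and it leaves each site to notice the statement in the risk narrative.

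A second reply is that fibrate exposure at ages 12 to 17 may be rare, so the gap may affect nobody. That also stands as far as it goes. The documents give no figure for past fibrate use, and any percentage would be a guess. The sub-study requires a history of hypertriglyceridemia (Section 13.1), which may make earlier lipid treatment likelier in those 10 participants, but that is inference.

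Two stronger readings are tempting, and the documents do not support them.

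- **Contraception as a second contradiction.** Section 2.3.1 says "gemcabene should not be administered to pregnant women or women of childbearing potential not using effective methods to prevent pregnancy", while exclusion 19 opens "Sexually active female participants of childbearing potential and Tanner stage". A reader might infer that girls who are not sexually active are wrongly admitted. But effective methods can be read to include abstinence, and on that reading exclusion 19 applies the warning. Exclusion 10, the pregnancy tests at Baseline and Weeks 2, 6 and 12 in Table 1, and the stopping rule in Section 8.3.9 also carry the concern into the plan. The two passages can be read consistently.
- **Distortion of the safety results.** A reader might infer that one foreseeable reaction would distort them. Section 9.4.4 plans counts and percentages with 95% confidence intervals. One event among the 40 planned participants would be 1/40 = 2.5%, reported as such. That is an event to avoid for the child's sake, not a bias in the analysis.

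**Conclusion.** The inconsistency holds as a narrow one. Section 2.3.1 advises against gemcabene in a defined group, and Section 5.2 as written does not exclude that group. The conclusion rests on the text of the two sections and on the absence of any other provision that fills the gap; it needs no assumption about event rates.

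Its size in numbers is unknown and probably very small. It does not touch the primary endpoint, its test or the sample size. It is worth correcting because the consequence would fall on an individual child and the correction is cheap. The documents do not show that any such child would in practice be enrolled, nor which of the two sections reflects the sponsor's intention.

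**What to change.** Reconcile Sections 2.3.1 and 5.2 before enrolment, in one of two ways:

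- the eligibility list carries the protocol's own statement on fibrate hypersensitivity and past significant reactions; or
- the protocol states why that statement does not apply to eligibility in this trial.

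The choice is a clinical one for the sponsor's safety team. If the statement becomes a criterion, it can be checked in the medical history already taken at Screening, so no new visit, test or form is needed. The cost is about one line of text and any additional screen failures. Their number cannot be derived from the documents but should be very small. The sample size and the analysis plan do not change.
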